SPONSOR: Bank of Cyprus Oncology Centre

COLLABORATOR: Merck Sharp & Dohme (MSD)

TITLE: A Phase II study of SWItch Maintenance PEmbrolizumab in patients with non small cell lung cancer who do not progress after first line platinum doublet chemotherapy (SWIPE).

IND NUMBER: 3475-449

EudraCT NUMBER: 2016-000857-11

NCT 02705820

**Study Principal
Investigator**

[name] BM MRCP FRCR

Consultant Clinical Oncologist

Bank of Cyprus Oncology Centre

[name]

[name]

Nicosia – Cyprus

[contact] (secretary)

[contact]

E-mail: [contact]

Protocol Version	Date of Regulatory Approval	Amendment Reference
1.0 - dated February, 2016	27 May, 2016	-
1.1- dated 16 June, 2017	10 July, 2017	No. 1 Scientific

TRIAL SUMMARY

[figure not shown]
Abbreviated Title	Maintenance Pembrolizumab in patients with Non Small Cell Lung Cancer (NSCLC)
Trial Phase	Phase II
Clinical Indication	For patients with no disease progression after first line chemotherapy
Trial Type	Single arm, one stage, Phase II trial
Type of control	Non randomized
Route of administration	Intravenous
Trial Blinding	Not applicable
Treatment Groups	Single group
Number of trial subjects	Forty eight (48)
Estimated enrollment period	April 2016- October 2017
Estimated duration of trial	Three and a half (3 ½) years
Duration of Participation	Two (2) years
Estimated average length of treatment per patient	6 cycles

1.0 TRIAL DESIGN

1.1 Trial Design

Single arm one stage Phase II study: post 4-6 cycles platinum doublet chemotherapy for patients with metastatic Non Small Cell Lung Cancer (NSCLC) offering Pembrolizumab as maintenance therapy to non-progressors with primary endpoint: Immune Related Progression Free Survival (irPFS) at 1 year. Aim to show that this is at least 25% (compared to an expected 12% 1 year PFS based on the Pemetrexed and Erlotinib maintenance trials).

1.2 Trial Diagram

2.0 OBJECTIVE(S) & HYPOTHESIS(ES)

2.1 Primary Objective(s) & Hypothesis(es)

Objective: The main objective of this trial is to provide efficacy data for Pembrolizumab as maintenance therapy after first line therapy for NSCLC. Especially relevant would be evidence of a higher percentage of patients being progression free at 1 year (primary endpoint), increased response rates, increased Progression free and Overall Survival (OS) compared to the results from other chemotherapy maintenance studies.

Hypothesis: Pembrolizumab can provide superior outcomes in terms of disease control (% of patients Progression Free at 1 year using Immune Related response criteria) compared to other maintenance treatments (specifically pemetrexed continuation maintenance for non-squamous NSCLC and erlotinib switch maintenance for squamous NSCLC).

2.2 Secondary Objective(s) & Hypothesis

Objective: Pembrolizumab can provide superior outcomes in terms of disease control / survival compared to its use in other lines of therapy.

Hypothesis: The secondary study hypothesis is that Pembrolizumab is going to have its biggest impact in patients with metastatic NSCLC, if used in the maintenance setting, i.e. potentially superior outcomes to being used either as first line or last line therapy (as has been tested until now).

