3.1.4 Pembrolizumab: Preclinical and Clinical Trial Data

KeytrudaTM Pembrolizumab is a potent and highly selective humanized monoclonal antibody (mAb) of the IgG4/kappa isotype designed to directly block the interaction between PD-1 and its ligands, PD-L1 and PD-L2. By blocking the binding of PDL-1 and 2 with the PD-1 receptor on the surface of activated T-cells, and consequently increase T-cell activation by removing the inhibitory signaling of PD-1²⁵.

KeytrudaTM (pembrolizumab) has been approved in the United States for the treatment of patients with unresectable or metastatic melanoma and disease progression following ipilimumab and, if BRAF V600 mutation positive, a BRAF inhibitor, and has also received accelerated approval to treat patients with advanced (metastatic) non-small cell lung cancer

SWIPE Protocol Version: 1.1 June, 2017

(NSCLC) whose disease has progressed after other treatments and with tumors that express PD-L1.

In the recent publication of the KEYNOTE-001 trial²⁶, including 495 patients, both treatment-naïve and previously treated advanced NSCLC patients, the overall response rate (ORR) was 19.4% and the median duration of response was 12.5 months. The median duration of progression-free survival was 3.7 months, and the median duration of overall survival was 12.0 months. Patients who were treatment naïve had better response rates (RRs): 24.8% compared to 18.0% for the previously treated patients. Equally median PFS was higher in untreated patients: 6 months versus 3 months for the previously treated patients. Finally for patients with greater than 50% PDL1 expression on immunohistochemistry the RR was 42.5%, median progression-free survival was 6.3 months, whilst median overall survival was not reached.

Similar to the KEYNOTE -001 data with Pembrolizumab, clinical trials with other anti-PD-1 and anti-PD-L1 antibodies show similar efficacy producing durable responses in approximately 20% of unselected patients with advanced NSCLC²⁶.

Refer to the Investigator's Brochure for further Preclinical and Clinical data²⁷.

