With this study, looking at efficacy and tolerability of Pembrolizumab as maintenance therapy after first line therapy for NSCLC, it is hoped that evidence of better efficacy is going to be generated compared to other chemotherapy maintenance studies and compared to the use of Pembrolizumab in other lines of therapy. This should lead to further studies to establish the role of Pembrolizumab as maintenance therapy in NSCLC, potentially providing better treatments and outcomes for patients with advanced NSCLC.

Finally, it is worth reflecting on the reality of access to innovative new drugs for Lung Cancer patients in Cyprus, whilst maintenance Pemetrexed is also not available due to funding restrictions. As a result, this study provides access to Pembrolizumab, a very important checkpoint inhibitor in NSCLC, as a maintenance treatment, where no other treatment options are available for patients with advanced NSCLC, in Cyprus.

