4.0 METHODOLOGY

4.1 Entry Criteria

4.1.1 Diagnosis/Condition for Entry into the Trial

In order to be eligible for trial entry, patients must have a diagnosis of metastatic Non Small Cell Lung Cancer, and should not have progressed after first line palliative chemotherapy with a platinum doublet. They should have received no more than six (6) cycles of a platinum doublet chemotherapy, and should be able to receive treatment within three (3) to six (6) weeks from the last chemotherapy administration.

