7.0 STATISTICAL ANALYSIS PLAN

7.1 Statistical Analysis Plan Summary

The study employs a one stage phase II Fleming's design using irPFS at 1 year as primary endpoint.

Using response hypotheses of $H_0 < 12\%$ and $H_a > 25\%$ i.e. that the irPFS at 1 year for the maintenance Pembrolizumab arm is 25%, compared to 12% in the normal chemotherapy maintenance arm, with a significance level (i.e., the probability of rejecting H_0 when it is true) $\alpha=0.05$ and the power (i.e. the probability of deciding the regimen is active) is 0.8 when true response rate is 25%, 48 patients are required to be entered into this study.

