7.2 Statistical Analysis Plan

Comparator data regarding patients' outcomes receiving maintenance therapy can be obtained from the Pemetrexed continuation and Erlotinib switch maintenance studies.

The best available data for maintenance treatment of non-squamous NSCLC patients come from the continuation Pemetrexed trial (Pas Ares¹⁶). This trial enrolled good performance status patients (PS 0-1), with non-squamous histology, who did not progress after 4 cycles of Pemetrexed / Cisplatin, and continued Pemetrexed chemotherapy, resulting in a 1-year PFS of 18.6%, whilst in the placebo arm the 1 year PFS was 5%.

For the squamous patients, the best available data come from the switch maintenance Erlotinib trial²¹ (SATURN), given that Erlotinib is the only agent approved for maintenance treatment in patients with squamous cancers. The 1-year PFS for the erlotinib arm is slightly above placebo, around 6%.

Hence for the comparator arm by using:

- data from the Pemetrexed continuation study for non squamous histology: 1-year PFS of 18% for non squamous on Pemetrexed maintenance,
- data from the erlotinib arm in the SATURN trial for patients with squamous histology and estimating 1-year PFS of 6% for squamous patients
- whilst assuming a ratio of 1:1 adenocarcinomas to squamous,
- provides us a weighted average of 12% of 1-year PFS

Assume irPFS at 1 year for the maintenance Pembrolizumab arm to be 25%, compared to 12% in the normal chemotherapy maintenance arm.

Sample size for Fleming one stage Phase II trials

Probability of Type I Error (α) = 0.05

Power ($1 - \beta$) = 0.8

Lower proportion for rejection (p_0) = 0.12

Higher proportion for acceptance (p_n) = 0.25

Sample size required = 48

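### Section 2.2 sets out to show that pembrolizumab does better as maintenance than in other lines, which one arm of selected non-progressors with no planned comparison cannot answer

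*Combined protocol and SAP*

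**What the plan says.** Section 2.2 has two sentences. The objective states, without qualification, that maintenance use gives better disease control and survival than use in other lines. The hypothesis is softer and speaks of "potentially superior outcomes to being used either as first line or last line therapy". The closing part of section 3.2.1 hopes the study will yield evidence of better efficacy both against chemotherapy maintenance and "compared to the use of Pembrolizumab in other lines of therapy".

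The trial summary describes a "Single arm, one stage, Phase II trial", non-randomized. Under section 4.1.1, patients "should not have progressed after first line palliative chemotherapy with a platinum doublet". Section 3.2.3.1 starts the 1-year clock at enrolment and first maintenance dose.

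Sections 7.1 and 7.2 plan a single test, on the primary endpoint: "Assume irPFS at 1 year for the maintenance Pembrolizumab arm to be 25%, compared to 12% in the normal chemotherapy maintenance arm". The 12% averages pemetrexed (18%) and erlotinib (6%) maintenance. Nothing in the SAP refers to pembrolizumab in another line. The only PFS figures split by prior treatment are in section 3.1.4, from a cited pembrolizumab series: "Equally median PFS was higher in untreated patients: 6 months versus 3 months for the previously treated patients".

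**The concern.** A superiority objective needs something to be superior to, and a way to separate the effect of timing from differences between the patients compared. The plan has neither.

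The arm contains only patients who came through induction without progression. Anyone who progressed or died during induction is absent, and the clock starts after that period. The protocol describes the resulting prognostic gap itself: the numbered reasons 3 and 4 in section 3.2.1 say that maintenance candidates already have a response or stable disease and less tumour, while patients after two or three lines tend to progress fast. A better result than in later lines is therefore expected even if timing makes no difference to how well the drug works.

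At stake is what the trial may conclude. If the objective stays as written, a higher 1-year figure than published later-line results could be reported as meeting a prespecified secondary objective, although selection might explain it.

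**Working it through.** **Inputs from the documents.** p0 = 12%, p1 = 25%, alpha 0.05, power 0.80, n = 48 (sections 7.1 and 7.2). Pembrolizumab median PFS is 6 months untreated and 3 months previously treated (section 3.1.4). Induction is 4 to 6 cycles (section 1.1), with 3 to 6 weeks from last chemotherapy to first dose (section 4.1.1).

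**Assumptions, not in the documents.** The shape of the PFS curve, a 3-week chemotherapy cycle, and the share q of patients starting chemotherapy who reach maintenance without progression.

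1. **The plan's own figure.** n = [(1.645·√(0.12·0.88) + 0.842·√(0.25·0.75)) / (0.25 − 0.12)]² = 47.8, so 48. This reproduces with a one-sided alpha. It sizes the primary test only.

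2. **First-line figure at 1 year.** None is given. With a constant hazard, the 6-month median gives 0.5^(12/6) = 25%. With a Weibull curve, 0.5^((12/6)^k) gives:

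| Shape k | 0.6 | 0.8 | 1.0 | 1.2 | 1.3 |
|---|---|---|---|---|---|
| 1-year PFS | 35% | 30% | 25% | 20% | 18% |

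3. **Could 48 patients separate maintenance from that figure?** An observed 12/48 = 25% has an exact 95% CI of 13.6% to 39.6%, which covers the whole 18% to 35% range. Taking 25% as a fixed reference, excluding it one-sided at 0.05 needs at least 18/48 (37.5%; exact tail probability 0.037). The chance of reaching 18 is 3.7% at a true rate of 25%, 41% at 35%, 69% at 40% and 88% at 45%. These figures ignore sampling error in the reference.

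4. **Later-line figure.** With a constant hazard, the 3-month median gives 0.5^(12/3) = 6.25% (1.5% to 20% for shapes 1.3 to 0.6). Excluding 6.25% needs only 7/48 (exact tail probability 0.029), and at a true 25% the chance of that is 97%. A naive comparison with later-line use would thus very likely look positive at the design alternative, and this is the comparison in which section 3.2.1 itself describes the largest prognostic difference.

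5. **Direction against first-line use.** Maintenance starts (cycles − 1)·3 + gap weeks after chemotherapy starts. That is 9 + 3 = 12 weeks (2.76 months) at the earliest and 15 + 6 = 21 weeks (4.83 months) at the latest. At 12 months after that point, the constant-hazard first-line curve stands at 0.5^(14.76/6) = 18% to 0.5^(16.83/6) = 14%. On the same clock, counting everyone who starts chemotherapy, a 25% maintenance rate becomes 0.25·q: 12.5% at q = 0.5, 15% at 0.6, 17.5% at 0.7, 20% at 0.8. The two are equal at q = 0.143/0.25 = 0.57 to q = 0.182/0.25 = 0.73. Below that range first-line use looks better, and above it maintenance does. The plan gives no q and does not estimate one.

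**The case against.** The strongest reply is that nothing in the plan acts on section 2.2. The hypothesis is hedged, section 3.2.1 only expresses a hope and looks ahead to further studies, and section 3.2.3.1 already lists response, PFS, irPFS and OS as secondary endpoints without a comparative test. No decision rule depends on the comparison. This is fair, and it keeps the point to one of wording. It does not rescue the objective sentence, which asserts superiority plainly.

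Four stronger readings are tempting, and the documents do not support them.

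- **That the 25% target shows maintenance has no advantage over first-line use.** The match with 25% comes from a rounded median and a constant hazard. The target was set against the 12% maintenance benchmark, with no reference to first-line pembrolizumab. It is also an irPFS rate, which requires confirmed progression (section 10.3), whereas section 3.1.4 does not say which criteria its median used.
- **That maintenance does worse once induction losses are counted.** Setting 15% to 20% of all chemotherapy starters (q of 0.6 to 0.8) against a first-line 25% mixes two time origins. On a common clock the first-line figure is 14% to 18%, and the implied deficit disappears.
- **That the comparison is biased in favour of the drug.** Both sides are pembrolizumab. Selection would favour maintenance timing, and the documents do not show whether it accounts for part or all of any difference.
- **That the primary analysis is undermined.** It tests a different benchmark and does not use this comparison.

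Section 3.1.4 also gives too little about entry and time origin in the cited series to measure the selection difference.

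**Conclusion.** The point holds as a limit on what may be concluded. One non-randomized arm of non-progressors, timed from the first maintenance dose and with no planned analysis against other lines, cannot support the superiority stated in section 2.2. That follows from the design and needs no assumption.

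Against later-line use, an advantage is expected from selection alone. Against first-line use, even the sign is open: with a constant hazard and 3-week cycles it turns at a non-progressing share of about 57% to 73%. The precision is also too low, since an observed 25% is compatible with any first-line rate in the assumed 18% to 35% range.

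The sizes are illustrations resting on the assumed curve shape. They are not estimates of bias, and the primary test of 25% against 12% is not affected.

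**What to change.** Reword section 2.2 as a descriptive, hypothesis-generating objective: estimate irPFS, PFS and OS with confidence intervals from the first maintenance dose. If published figures for pembrolizumab in other lines are shown, present them as context only, with their entry criteria, time origin and response criteria beside them. State in sections 2.2 and 3.2.1 that no superiority over first-line or last-line use will be concluded from this trial.

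The endpoints are already listed in section 3.2.3.1, so no patients, visits or sample size change. The cost is a wording amendment and the loss of a secondary claim that the design cannot support.

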2.3 Exploratory Objective

Objective: Document change in PDL1 expression on CTCs, plasma and histology, prior and during first line chemotherapy as well as during immunotherapy with Pembrolizumab, in patients with non progressive disease, and determine patterns of change suggestive of benefit to Pembrolizumab.

3.0 BACKGROUND & RATIONALE

3.1 Background

Based on the GLOBOCAN data, Lung Cancer is the commonest cancer worldwide with 1.8 million cases being diagnosed in 2012, as well as the most common cause of cancer death with 1.6 million deaths worldwide¹. There are two main subdivisions of Lung Cancer; small cell lung cancer (SCLC) and non-small cell lung cancer (NSCLC). This study is focused in the treatment of NSCLC, which accounts for approximately 80% of all lung cancers. Although over the last few years there have been a number of new drugs (EGFR / ALK Tyrosine Kinase Inhibitors) and technology developments (e.g. stereotactic ablative radiotherapy and intensity modulated and image guided radiotherapy) in the treatment of NSCLC and there are now a wide range of different treatments available to patients with

NSCLC, survival still remains very poor with only approximately about 10% of patients being alive five year after the initial diagnosis¹. There is therefore an urgent need to introduce new innovative treatments for patients with NSCLC in order to improve outcomes in this disease.

3.1.1 Therapeutic Background

Information for metastatic Non Small Cell Lung Cancer (NSCLC)

Routine molecular testing is currently being carried out for patients with metastatic NSCLC: predominantly checking for EGFR mutations and ALK translocations. Patients with such genetic alterations are candidates to receive either EGFR Tyrosine Kinase Inbitors (TKIs) i.e. Erlotinib, Gefitinib or Afatinib, if they harbour an EGFR mutation or Crizotinib if they have an ALK translocation².

For patients with metastatic NSCLC and good performance status (WHO PS 0-2), without EGFR mutations or ALK translocations, the ESMO guidelines recommend first line treatment with a platinum doublet². A phase III trial suggested superior outcomes for the combination of pemetrexed cisplatin versus gemcitabine cisplatin in patients with non-squamous NSCLC, whilst for patients with squamous cancers gemcitabine cisplatin provided better outcomes³. More specifically overall survival was statistically superior for cisplatin/pemetrexed versus cisplatin/gemcitabine in patients with adenocarcinoma (n = 847; 12.6 v 10.9 months, respectively) and large-cell carcinoma histology (n = 153; 10.4 v 6.7 months, respectively), whilst in patients with squamous cell histology, there was a significant improvement in survival with cisplatin/gemcitabine versus cisplatin/pemetrexed (n = 473; 10.8 v 9.4 months, respectively). Equally in the ECOG 4599 trial⁴, the addition of Bevacizumab (Avastin) in combination with carboplatin and paclitaxel showed a significant improvement in overall survival to 12.3 months compared to 10.3 months with the same regimen without Bevacizumab (hazard ratio for death, 0.79; P=0.003) in patients with non squamous NSCLC (also excluding patients with significant haemoptysis and brain metastases). Other large phase III trials comparing different platinum based regimens in the first line setting or non platinum versus platinum doublets, or addition of molecularly targeted drugs , e.g. the EGFR inhibitors such as Iressa (gefitinib) in the INTACT1 and 2 trials and Tarceva (erlotinib) in the TALENT and TRIBUTE trials to chemotherapy failed to show an improvement in overall survival compared to cytotoxic chemotherapy alone².

As a result of these studies, first line chemotherapy for patients with non-squamous metastatic NSCLC without EGFR mutations or ALK translocations is either pemetrexed platinum chemotherapy (preferred in Europe) or Carboplatin Paclitaxel and Bevacizumab (preferred in the USA). For squamous cancers a non- pemetrexed / non- bevacizumab platinum doublet, often platinum gemcitabine, is used worldwide.

In the second line setting Docetaxel was the first drug to be approved following a landmark randomized control study versus best supportive care showing an improvement in median survival from 4.6 to 7 months⁵. However this was at considerable toxicity especially in terms of severe neutropaenia and malaise. The next step to second line therapy was the randomized

controlled study of Docetaxel versus pemetrexed, which showed similar response rates and overall survival for the two agents⁶. It was also noted that pemetrexed had significantly less toxicity than Docetaxel, especially in terms of severe neutropaenia, febrile neutropaenia, deaths due to neutropaenia and hospitalization rates.

The next agent to gain approval both for second and third line use was Erlotinib (Tarceva) based on the BR21 trial; a randomized controlled versus placebo study showing an improvement in survival from 4.7 to 6.7 months⁷. In this trial eligible patients were those that had either already received first and second line therapy, or had received only first line therapy but were not deemed fit to receive further palliative chemotherapy.

More recently in the last two years, data have supported the use of two novel anti-angiogenic agents, nintedanib and ramucirumab, both in conjunction with docetaxel, as second line treatment for metastatic NSCLC. In the LUME-Lung I trial⁸, 1314 patients were randomized to docetaxel with or without nintedanib, with the combination improving overall survival in adenocarcinoma patients with a median of 12.6 versus 10.3 months respectively. In the REVEL trial⁹, 1253 patients were randomized to docetaxel with or without ramucirumab, with the combination improving overall survival from a median of 9.1 months to 10.5 months. In this study with ramucirumab the benefit was also seen in patients with squamous histology; this is the first evidence of benefit of an antiangiogenic monoclonal antibody for patients with squamous Lung Cancer.

3.1.2 Background data: Maintenance Chemotherapy in NSCLC:

With the understanding that we have reached a therapeutic plateau with platinum doublet first line chemotherapy in NSCLC, there has been renewed interest in “maintenance” therapy in metastatic NSCLC in the last few years^{10 11}. Maintenance therapy is applied after 4-6 cycles of chemotherapy to patients who have not progressed after the initial chemotherapy. Distinction needs to be made between continuation and switch maintenance. According to the NCCN (National Comprehensive Cancer Network) guidelines, continuation maintenance refers to the use of at least one of the agents used in first line, whilst switch maintenance refers to the initiation of a different agent, not included as part of the first line regimen.

Given that the main toxicity from platinum doublet chemotherapy is due to the platinum agent (especially cisplatin), a number of investigators have looked at the possibility of continuing with the non platinum agent¹⁰. Such trials include continuation of Paclitaxel (Belani 2003¹²), Gemcitabine (Brodowicz 2006¹³, Belani 2010¹⁴ and Perol 2010¹⁵), and Pemetrexed (Paz Ares 2011¹⁶). The design of all these trials is that they randomized non progressors after 4 cycles (or 16 weeks in the case of the paclitaxel trial) of chemotherapy to continuing with the non platinum agent until progression. From these trials only the continuation maintenance Pemetrexed trial by Paz Ares showed a statistically significant overall survival difference (from 11.0 to 13.9 months; 22% reduction of risk of death with HR=0.78 and 95% CI: 0.64 to 0.96; P=.0195) for patients with non-squamous NSCLC.

In terms of continuation maintenance of targeted agents, the licensing studies for both Bevacizumab (ECOG 4599 by Sandler⁴) and Cetuximab (the FLEX trial by Pirker¹⁷) specified continuation of both agents until progression, and beyond the initial chemotherapy doublet treatment period, hence both cetuximab and bevacizumab if used with the initial chemotherapy doublet, need to be continued until disease progression (although no randomization to a continuation versus no continuation Bevacizumab or Cetuximab was tested in these trials).

In terms of switch maintenance, there have been six (6) randomized trials in the last five years. The common theme in these trials, is that they randomized non progressors after four cycles of first line platinum doublet chemotherapy to immediate treatment with one of four agents already licensed for use as second line therapies in NSCLC, i.e. pemetrexed¹⁸, docetaxel¹⁹, gefitinib²⁰, erlotinib alone²¹ and erlotinib in combination with bevacizumab²² in patients receiving bevacizumab as part of their first line treatment, versus treatment at progression, and also to vinorelbine²³. From the chemotherapy switch maintenance trials, there was only one positive trial for overall survival with pemetrexed. In the Pemetrexed / JMEN trial¹⁸, Ciuleanu et al, randomized 663 patients with advanced NSCLC who had not progressed after four cycles of platinum-based chemotherapy (which did not include pemetrexed) to Pemetrexed versus placebo, showing an improvement in PFS (4 vs. 2 months; $p < .00001$) and OS (median 13.4 versus 10.6 months, $p = .012$). As the trial was enacted prior to the understanding of the treatment interaction by histology for pemetrexed, squamous cell cancers were also included. Patients with squamous histology however derived no benefit from pemetrexed, and subset analysis looking at patients with nonsquamous histology showed a large, 5.2 month survival benefit for maintenance Pemetrexed versus placebo. The main criticism about this trial was that 33% of the patients in the observation arm did not receive second-line chemotherapy, whilst only 19% of the patients who received chemotherapy received pemetrexed at the time of progression.

From the switch maintenance trials with targeted agents, there was only one positive trial; the SATURN trial²¹ by Capuzzo, which tested the benefit of immediate Erlotinib for patients who had not progressed after four cycles of platinum-based first-line chemotherapy. Erlotinib maintenance therapy significantly improved progression free and overall survival although the absolute difference in median OS was modest of only one month from 11 to 12 months. Both patients with EGFR mutations and wild type patients appeared to benefit. Further analysis of this trial, showed that the main benefit was seen in patients with stable disease (SD) after first line chemotherapy, who had a 2.3 month improvement in median survival. These results led to the approval for Erlotinib for switch maintenance to be limited to patients with SD after induction treatment². Similar to the Pemetrexed trial, there is criticism that only 21% of patients on the placebo arm ever got an EGFR inhibitor like Erlotinib.

As a result of these studies recently there is more interest in providing maintenance therapy to patients with advanced NSCLC, especially for patients with non-squamous histology (where both Pemetrexed as continuation and switch maintenance can be used). For patients with squamous histology, this approach is less commonly applied given the limited benefit seen in the randomized studies (small benefit found for patients with stable disease after first line chemotherapy, by using erlotinib in the SATURN trial²¹). The most common clinical practice pattern in Europe regarding maintenance therapy is the use of continuation maintenance therapy for patients with non-squamous histology with Pemetrexed trial (Paz Ares et al¹⁶). Equally clinically meaningful improvement in survival has been seen with the switch maintenance trial for Pemetrexed (starting with a non-Pemetrexed containing regimen) again for patients with non-squamous cancers (Ciulianu T et al¹⁸), however this approach is not commonly used.

Despite the use of various lines of chemotherapy, including maintenance chemotherapy, the benefit seen with these treatments is modest, with median survival for patients with metastatic NSCLC remaining approximately 1 year²⁴. There is therefore an urgent unmet need to provide new / innovative therapies to patients with metastatic NSCLC, that are going to have a bigger impact and more specifically that are going to be able to provide them with more durable responses and lasting disease control. **Immunotherapy checkpoint inhibitors have shown very promising results in a number of different cancer types, including Non Small Cell Lung Cancer, and are coming to the forefront to address this need, which is the reason for this study.**

